6.3. Vital Signs and Physical Examination Findings

Vital signs variables including heart rate, blood pressure (systolic and diastolic) will be measured at visits as per the schedule of events in the protocol. Descriptive statistics of the observed value and change from baseline of the vital signs will be summarized by treatment group.

Physical exam findings will not be analyzed except that they are captured as AEs and are included in the analyses of AEs.

6.4. Electrocardiogram

A supine 12-lead ECG will be performed at Weeks 0, 16, and 48, as specified in the Time and Events Schedule. Electrocardiogram data will be summarized by ECG parameter. Descriptive statistics will be calculated at baseline and for observed values and change from baseline at each scheduled time point.

In addition, summary of post-baseline ECG abnormalities different from Week 0 and a listing of subjects with any post-baseline ECG abnormalities different from Week 0 measurement will be provided.

6.5. Electronic Columbia-Suicide Severity Rating Scale (eC-SSRS)

The electronic Columbia-Suicide Severity Rating Scale (eC-SSRS) will be used as a screening tool to prospectively evaluate the potential of guselkumab to induce suicidal ideation and behavior. The eC-SSRS defines five subtypes of suicidal ideation and behavior in addition to self-injurious behavior with no suicidal intent, and is a fully-structured subject self-report questionnaire, including standardized questions, follow-up prompts, error handling routines, and scoring conventions. The Screening version of the eC-SSRS will be conducted at Screening followed by the Since Last Visit version of the eC-SSRS at all other visits through Week 56 except at Week 1, 2, and 3.

The eC-SSRS will be performed during each evaluation visit according to the assessment schedule. The eC-SSRS will be performed at screening after signing informed consent, and before study agent administration, and as the first assessment for all post-baseline visits. The baseline is defined as the most severe/maximum eC-SSRS score at either screening or Week 0.

In addition, potential suicide related adverse events including suicidal ideation, suicidal behavior excluding completed suicide, and completed suicide will be identified by the investigators and collected in the eCRF.

The following are eC-SSRS categories and have binary responses (yes/no). A “yes” response to any eC-SSRS category will be assigned a score as below:

Suicidal Ideation (1-5)

1 = Wish to be Dead

2 = Non-specific Active Suicidal Thoughts

3 = Active Suicidal Ideation with Any Methods (Not Plan) without Intent to Act

4 = Active Suicidal Ideation with Some Intent to Act, without Specific Plan

5 = Active Suicidal Ideation with Specific Plan and Intent

Suicidal Behavior (6-10)

6 = Preparatory Acts or Behavior

7 = Aborted Attempt

8 = Interrupted Attempt

9 = Actual Attempt (non-fatal)

10 = Completed Suicide

If no events qualify for a score of 1 to 10, a score of 0 will be assigned (0 = “Negative result [no suicidal ideation or behavior]”). Higher scores indicate greater severity.

The summary for suicidal ideation and behavior will be based on the safety analysis set. Suicidal ideation and behavior will be summarized based on the most severe/maximum post baseline eC-SSRS outcome or AE of suicidal ideation, suicidal behavior excluding completed suicide, or completed suicide through Week 56.

The maximum score assigned for each subject will also be summarized into one of three broad categories: No suicidal ideation or behavior, suicidal ideation, suicidal behavior. A shift table for change in eC-SSRS categories of no suicidal ideation or behavior, suicidal ideation, and suicidal behavior from baseline through Week 56 will be presented, where the baseline category is based on eC-SSRS score and the post baseline is based on eC-SSRS or AE data.

7. PHARMACOKINETICS/IMMUNOGENICITY

7.1. Pharmacokinetics

Blood samples for measuring serum guselkumab concentrations (pre-injection if it is injection visit) will be collected from all subjects at scheduled visits as indicated in the Time and Events Schedule in the protocol.

The PK analysis will be based on subjects who received at least 1 administration of guselkumab and had at least one evaluable serum sample. No imputation of missing concentration data will be performed, that is, data summaries will be based on the observed data.

All concentrations below the lowest quantifiable concentration in a sample or missing data will be labeled as such in the concentration data listings or Statistical Analysis Software™ dataset. Concentrations below the lowest quantifiable concentration in a sample will be treated as zero in the summary statistics. All subjects and samples excluded from the analysis will be clearly documented.

For analysis of serum guselkumab concentrations, descriptive statistics, including arithmetic mean, SD, median, interquartile range, minimum, and maximum will be calculated at each scheduled sampling time point for the guselkumab group. The PK concentration data may be displayed graphically.

All summaries for serum guselkumab concentration will exclude data collected after subjects (1) did not receive a scheduled guselkumab administration within ± 14 days of the protocol scheduled dosing date, or those subjects who discontinued study agent, (2) received a partial, incorrect, or an additional guselkumab administration, (3) or have invalid sample data if the sample is taken after study agent administration or a concentration value falls outside the predefined range ($\pm 10 \times SD$). Of note, serum guselkumab concentrations prior to the first of such events will be included in the summaries.

If needed, a population PK analysis using a nonlinear mixed-effects modeling approach will be used to characterize the disposition characteristics of guselkumab in the current study. Data may be combined with those from pivotal Phase 3 studies (CNTO1959PSO3001 and CNTO1959PSO3002) to support a relevant structural model. Details will be given in a

population PK analysis plan and results of the population PK analysis will be presented in a separate technical report.

The effect of serum guselkumab concentrations on efficacy of guselkumab will be explored.

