
FOOTNOTES:
 
a: The screening visit should occur within approximately 4 weeks before the Week 0 visit.
 
b: All Week 48 study procedures should be performed on any subject who terminates the study prior to Week 48, except for collection of serum for biomarkers. If a subject terminates post-Week 48, sites should make every effort to conduct the Week 56 assessments.
 
c: All study procedures and evaluations should be completed before administration of study drug. Assessments for subjects who discontinue study agent administration or withdraw from the study are discussed in Section 10.2.
 
d: Women of childbearing potential must have a negative urine pregnancy test before randomization, before study drug administration, and at all study visits.
 
e: The eC-SSRS should be completed by the subject before any tests, procedures, or other consultations to prevent influencing subject perceptions,
 
f: A tuberculin skin test is additionally required if the QuantiFERON-TB Gold test is not approved/registered in the country in which this study is being conducted.
 
g: Laboratory tests are listed in Section 9.6.
 
h: Subjects must fast (ie, no food or beverages [except water]) for at least 8 hours before blood is drawn for lipid panel. All other visits can be nonfasting.
 
i: All blood samples must be collected before study agent administration at visits when a study agent administration is scheduled. Details will be provided in the Laboratory Manual.
 
j Serum biomarker measurements will include but are not limited to: serum IL-17A, IL-17F, and IL-22. For subjects who discontinue from the study prior to Week 48, serum is not to be collected for measurement of biomarkers.
 
k Biopsy samples for RNA and tissue histology will be collected only from subjects who consent to participate in the optional biopsy substudy. Biopsy samples will be used to assess the cellular and molecular profiles of psoriatic skin lesions at baseline and during treatment.
 
[REDACTED]
 
m: Blood samples for genetic (DNA) analyses will be collected only from subjects who sign a separate consent form to participate in the genetic (DNA) evaluations.
																		

ABBREVIATIONS

BCG	Bacille Calmette-Guérin
BSA	body surface area
CSR	clinical study report
DBL	database lock
ECG	electrocardiogram
eCRF	electronic case report form
eC-SSRS	electronic Columbia-Suicide Severity Rating Scale
eDC	electronic data capture

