2.4.3. Pharmacokinetics Analysis Set

The PK analysis set is defined as subjects who received at least one injection of guselkumab and have at least one valid blood sample drawn for PK analysis.

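### Read literally, the PK exclusion rule in SAP 7.1 lets one invalid sample remove all of that subject's later valid guselkumab concentrations; the rule should work per sample (minor).

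*SAP*

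**What the plan says.** The rule is one sentence in SAP 7.1. Its stem is "All summaries for serum guselkumab concentration will exclude data collected after subjects", and three items follow:

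- Item (1): a scheduled guselkumab dose not received within 14 days either side of its due date, or discontinuation of study agent.
- Item (2): the subject "received a partial, incorrect, or an additional guselkumab administration".
- Item (3): subjects who "have invalid sample data if the sample is taken after study agent administration or a concentration value falls outside the predefined range", the range being given as plus or minus 10 SD.

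The next sentence states what is kept: "serum guselkumab concentrations prior to the first of such events will be included in the summaries". It makes no distinction between the three items.

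The same section adds that "All subjects and samples excluded from the analysis will be clearly documented". SAP 2.4.3 admits a subject to the PK analysis set if, besides having received guselkumab, they "have at least one valid blood sample drawn for PK analysis". Footnote i of the protocol's Time and Events Schedule requires pre-dose sampling: "All blood samples must be collected before study agent administration at visits when a study agent administration is scheduled". Protocol 11.5 describes the concentration summaries and contains no exclusion rule.

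**The concern.** Items (1) and (2) change the dosing history, so concentrations after them no longer describe the planned regimen and a cut-off from that point is reasonable. Item (3) is different in kind, because it describes a fault in one tube or one assay result. A sample drawn a few minutes after the injection instead of before it leaves the next trough untouched. Yet item (3) shares the stem and the retention sentence with the dosing items, so a programmer who follows the text would drop every later sample from that subject.

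PK of guselkumab is a stated secondary objective (Protocol 2.1.1, SAP 1.1). Losses under this reading accumulate over visits, so the late summaries, Week 44 and Week 56, would rest on the fewest subjects. Two programmers could also implement different rules and both cite the SAP.

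**Working it through.** The plan states no figure on this point, so there is none to reproduce. The check has three parts.

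**1. Is the literal reading available, and does other text override it?** The stem governs all three items, and the retention sentence refers back to all of them. The documentation sentence in SAP 7.1 says exclusions will be recorded, not which samples are excluded. SAP 2.4.3 decides who enters the PK set, not which values enter the summaries. Protocol 11.5 is silent. Nothing overrides the literal reading.

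**2. What does one invalid sample cost?** The Time and Events Schedule puts guselkumab concentrations at Weeks 0, 4, 12, 20, 28, 44 and 56. All but Week 56 are dosing visits, so six draws must be pre-dose.

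| Invalid sample at | Later samples dropped | Of these, pre-dose troughs |
|---|---|---|
| Week 0 | 6 | 5 |
| Week 4 | 5 | 4 |
| Week 12 | 4 | 3 |
| Week 20 | 3 | 2 |
| Week 28 | 2 | 1 |
| Week 44 | 1 | 0 |
| Week 56 | 0 | 0 |

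A Week 0 tube drawn after the first injection would leave the subject with no concentration in any summary.

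**3. What is the expected loss?** Inputs:

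- n = 520, the planned guselkumab arm (SAP 1.4), taken as completely sampled.
- p, the chance that a pre-dose draw is mistimed. This is an assumption, because the documents give no rate. The range shown is 1% to 3%, independent across visits.

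An otherwise valid sample at the k-th post-baseline visit is lost if any of the k earlier draws was mistimed:

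loss(k) = 1 − (1 − p)^k, with k = 1 for Week 4 up to k = 6 for Week 56.

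At Week 56:

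- p = 1%: 1 − 0.99^6 = 5.9%; 520 × 0.0585 ≈ 30 lost, about 490 kept.
- p = 2%: 1 − 0.98^6 = 11.4%; 520 × 0.1142 ≈ 59 lost, about 461 kept.
- p = 3%: 1 − 0.97^6 = 16.7%; 520 × 0.1670 ≈ 87 lost, about 433 kept.

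Averaged over k = 1 to 6, the loss is 3.4%, 6.8% and 10.0%.

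If the loss is random and the SD is unchanged, the standard error of a visit mean grows by the factor 1/√(1 − loss). At Week 56:

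- p = 1%: 1/√0.941 = 1.03.
- p = 2%: 1/√0.886 = 1.06.
- p = 3%: 1/√0.833 = 1.10.

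Under a per-sample rule, the loss of other valid samples is zero at any p.

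**The case against.** The best defence is that no one would implement the sentence this way. Item (3) does not fit its stem grammatically. It carries its own condition and speaks of a single sample and a single value. The documentation sentence foresees excluding samples as well as subjects, and SAP 2.4.3 treats validity as a property of one blood sample. This stands as evidence that per-sample exclusion was probably intended. It does not settle the matter, because the retention sentence still points towards a cut-off.

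A second defence concerns the out-of-range limb. A value beyond 10 SD could come from a sample mix-up or an unrecorded dosing error, and dropping later data could then be a cautious choice. This also stands. The statement that later exposure is unaffected holds for a mistimed draw, not for every extreme value.

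Third, the consequence is small. The outputs are descriptive statistics by visit. The loss depends on an assumed rate, and random loss reduces numbers without biasing the mean. This stands too, and it sets the severity.

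A reader might also infer that the invalid value itself stays in the summaries, since it is neither before nor after its own event. The documents do not support that. The SAP calls the data invalid, and the only concentrations it affirmatively keeps are those before the event. No text includes the bad value.

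**Conclusion.** The point holds as a minor wording defect. SAP 7.1 as written permits, and on its literal terms directs, the loss of a subject's later valid concentrations after one mistimed or out-of-range sample, and no other text corrects it.

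The size is modest: at Week 56, a loss of 5.9% to 16.7% of otherwise valid samples and a standard error about 3% to 10% wider. These figures rest on an assumed mistiming rate of 1% to 3% per pre-dose draw, independence across visits, complete sampling of all 520 planned subjects, and an unchanged SD. They cover mistimed draws only; out-of-range values were not modelled.

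A reader might infer that the rule biases the PK results or weakens the trial's main conclusions. Neither follows. Independent random loss costs precision only, and the rule governs concentration summaries, so the efficacy tests, their power and their type I error are untouched. Any population PK analysis has its own plan. The planned explorations of concentration against efficacy (SAP 7.1) and of antibodies against PK (SAP 7.2) would be affected only if they used the same filtered data, which the SAP does not say.

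**What to change.** In SAP 7.1:

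- Apply the instruction to exclude data collected afterwards, and the sentence keeping data before the first event, to items (1) and (2) only.
- State separately that under item (3) only the invalid sample is excluded and the subject's other samples, before and after, are kept.
- Define a mistimed sample as one drawn after that visit's administration, since every post-baseline sample follows some dose.
- Add that if review of an out-of-range value reveals a dosing deviation, item (1) or (2) applies from that deviation.

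The cost is a few sentences and one sample-level programming flag. No new data are needed: actual sampling dates and times are already recorded (Protocol 9.7), and item (3) already requires invalid samples to be identified.

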7.2. Immunogenicity (Antibodies to Guselkumab)

Blood samples will be collected for the detection of antibodies to guselkumab at the specified visits as shown in the Time and Events schedule in the protocol.

The antibodies to guselkumab analysis will be based on subjects who receive at least 1 dose of guselkumab and have at least one samples collected post guselkumab administration for the detection of antibodies to guselkumab. No imputation of missing data will be performed, that is, data summaries will be based on the observed data.

The following analyses will be performed for guselkumab group as appropriate:

- Summary of antibodies to guselkumab status (incidence of positive antibodies to guselkumab and antibody titers)
- List of subjects positive for antibodies to guselkumab

In addition, the incidence of neutralizing antibodies (NAbs) to guselkumab will be summarized for subjects who are positive for antibodies to guselkumab and have samples evaluable for NAbs.

The effect of antibodies to guselkumab on PK, efficacy, and safety will be explored.

REFERENCES

ATTACHMENT

Attachment 1 Summary of Pooling Centers for Analysis

Site #	City	State/ Province	Country/ US Region	Number of Subjects Randomized	Sites to be combined	Number of Subjects per Pooled Site	Site Group
			Australia	5		15	
			Australia	2			
			Australia	3			
			Australia	5			
			Australia	7		14	
			Australia	7			
			Australia	3		11	
			Australia	8			
			Australia	1		18	
			Australia	17			
			Australia	13			
			Canada	7		15	
			Canada	8			
			Canada	10			
			Canada	10			
			Canada	10			
			Canada	15			
			Canada	9		19	
			Canada	5			
			Canada	5			
			Canada	10			
			Canada	24			
			Canada	25			
			Canada	10			
			Canada	10			

Site #	City	State/ Provin ce	Country/ US Region	Number of Subjects Randomized	Sites to be combined	Number of Subjects per Pooled Site	Site Group
			Czech Republic	4		11	
			Czech Republic	7			
			Czech Republic	5		16	
			Czech Republic	7			
			Czech Republic	4			
			Czech Republic	10		17	
			Czech Republic	7			
			Czech Republic	11			
			Spain	4		13	
			Spain	6			
			Spain	3			
			Spain	8		17	
			Spain	4			
			Spain	4			
			Spain	1			
			Spain	3		12	
			Spain	6			
			Spain	3			
			Spain	12			
			Spain	8		14	
			Spain	3			
			Spain	3			
			France	11			
			France	16			
			France	8		13	

Site #	City	State/ Provin ce	Country/ US Region	Number of Subjects Randomized	Sites to be combined	Number of Subjects per Pooled Site	Site Group
			France	2			
			France	3			
			France	18			
			Germany	7		19	
			Germany	12			
			Germany	5		15	
			Germany	4			
			Germany	6			
			Germany	9		22	
			Germany	5			
			Germany	8			
			Germany	4		15	
			Germany	8			
			Germany	3			
			Germany	7		13	
			Germany	6			
			Germany	15			
			Germany	10			
			Germany	5		13	
			Germany	8			
			Hungary	3		13	
			Hungary	9			
			Hungary	1			
			Hungary	6		16	
			Hungary	4			
			Hungary	6			
			Hungary	6		16	
			Hungary	7			

Site #	City	State/ Provin ce	Country/ US Region	Number of Subjects Randomized	Sites to be combined	Number of Subjects per Pooled Site	Site Group		
[REDACTED]	[REDACTED]	[REDACTED]	Hungary	3	[REDACTED]		[REDACTED]		
			Poland	20					
			Poland	20					
			Poland	10					
			Poland	10					
			Poland	10	[REDACTED]	13			
			Poland	3	[REDACTED]				
			Poland	30					
			Poland	11					
			Poland	10					
			Poland	18					
			Poland	15					
			Poland	20					
			Poland	29					
			Poland	4	[REDACTED]	13			
			Poland	9	[REDACTED]				
			Poland	19	[REDACTED]				
			[REDACTED]	[REDACTED]	United States	2		[REDACTED]	10
			[REDACTED]	[REDACTED]	United States	8		[REDACTED]	
			[REDACTED]	[REDACTED]	United States	1		[REDACTED]	10
[REDACTED]	[REDACTED]	United States	4	[REDACTED]					
[REDACTED]	[REDACTED]	United States	5	[REDACTED]					
[REDACTED]	[REDACTED]	United States	9	[REDACTED]	10				
[REDACTED]	[REDACTED]	United States	1	[REDACTED]					
[REDACTED]	[REDACTED]	United States	5	[REDACTED]	11				

Site #	City	State/ Provin ce	Country/ US Region	Number of Subjects Randomized	Sites to be combined	Number of Subjects per Pooled Site	Site Group
			United States	6			
			United States	9		23	
			United States	2			
			United States	4			
			United States	8			
			United States	4		25	
			United States	21			
			United States	3		14	
			United States	11			
			United States	4		14	
			United States	5			
			United States	2			
			United States	3			
			United States	4		16	
			United States	8			
			United States	4			
			United States	5		15	
			United States	7			
			United States	3			
			United States	1		19	

Site #	City	State/ Province	Country/ US Region	Number of Subjects Randomized	Sites to be combined	Number of Subjects per Pooled Site	Site Group		
[REDACTED]	[REDACTED]	[REDACTED]	United States	3	[REDACTED]	[REDACTED]	[REDACTED]		
			United States	4					
			United States	5					
			United States	1					
			United States	5					
			United States	3				13	[REDACTED]
			United States	10				20	[REDACTED]
			United States	19					[REDACTED]
			United States	5					[REDACTED]
			United States	3				14	[REDACTED]
			United States	10					[REDACTED]
			United States	2					[REDACTED]
			United States	9				[REDACTED]	[REDACTED]
			United States	4					[REDACTED]
			United States	1				[REDACTED]	[REDACTED]
